Figure E-2: Microinduction (Micro) vs. Treatment as Usual (TAU)

opioids report pain as the reason for their use, we will collect detailed data regarding opioid- and pain-related symptoms, and examine if these symptoms mediate the relationship between study arm and OUD outcomes.

B.8 Implementation and dissemination promise and challenges. A key implementation challenge is engaging low-income Black and Hispanic patients in BUP treatment.⁸⁵ Barriers include access to BUP and stigma of OUD treatment. We will collaborate with people with lived experience and the Stakeholder Board to minimize stigma, for example, with messaging that frames positive aspects of BUP treatment. Microdosing dissemination challenges include engaging hospital clinicians who have not had extensive training in addiction medicine. We will conduct qualitative interviews with clinical staff who support our research team in conducting the RCT to understand strategies for maintaining microdosing protocols once the study has been completed.

B.9 Expanding evidence of BUP cost-effectiveness. CP is associated with greater estimated costs than cancer, cardiovascular disease, and diabetes.⁸⁶ Total annual costs range from \$560 billion to \$635 billion annually in direct health expenditures and lost productivity. Hospitalization costs are also increasing. In a national sample, from 2011 to 2015, average costs per hospitalization for patients with OUD and CP increased from \$37,029 to \$47,480 even though length of stay remained stable between 5.74-5.82 days.⁶⁸ BUP treatment is known to be cost-effective, and has the potential to reduce hospital length of stay and re-hospitalization.⁸⁷ However, the 5-day microdosing protocol could also delay discharges. Examining how hospital-based microdosing affects re-hospitalization, acute care utilization and other health system or social costs would provide additional incentives for wide-spread implementation and dissemination of BUP microdosing.

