(on most or all days for ≥ 3 months) and at least moderate intensity and interference (score ≥ 4 on Pain, Enjoyment of Life and General Activity scale [PEG]).^{108,109} We will exclude patients who are currently receiving any OUD treatment (see **Table E-1**).

Table E-1: Inclusion and Exclusion Criteria

Inclusion Criteria	Exclusion Criteria

 • Age ≥ 18 years • Opioid misuse or OUD (see D.2.3) • Chronic pain (see D.2.3) • Currently taking opioids • Fluency in English or Spanish • Planned hospitalization for ≥ 48 hours 	
 • Current OUD treatment (BUP, methadone, naltrexone) • Severe alcohol or benzodiazepine use disorder • Hypersensitivity to BUP or naloxone • Pain due to malignancy • Severe untreated mental illness (suicidality, psychosis) • presence of an acute or chronic medical condition that would make participation medically hazardous • Resting respiratory rate >20 or O₂ saturation $<92\%$ • Pregnancy • Unable to consent due to pain or cognitive impairment

D.2.4 Recruitment:

We will actively and passively recruit hospitalized patients. Clinicians in the hospital, including pain and addiction consultants, will be informed about the study. Study information will be posted electronically and in common areas (e.g., physicians' lounges). [name], Director of Montefiore's Addiction Consult Service, and [name], Director of the Pain Service, will oversee recruitment of patients on whom they are consulted. Hospital Medical Directors will also assist in recruitment. We will also have the Epidemiology Informatic Unit (EISMU) produce daily recruitment data lists with identifiable information about hospitalized patients who have opioid use disorder and at least one chronic pain condition. We will contact the attending physician for hospitalized patients before approaching the patient for study recruitment. If given permission by the attending physician, the research coordinator will approach the hospitalized patient for recruitment.

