Table E-7 outlines the cost categories we will take into account when assessing incremental costs in each of the two reference case perspectives. We excluded cost categories not relevant to the timeframe of this study (e.g., impact on educational achievements). Because buprenorphine microdosing will occur during the index hospitalization only, we will not consider costs of patient time attending the intervention. The research team will have access to health insurance claims data for 40-50% of patients to be enrolled because their health plans make claims available to Montefiore for care management and research. For health care service costs, in addition to patient self-reports using validated questionnaires (see above) we will conduct a secondary analysis with these patients using the claims data, which are not subject to recall biases and not prone to missing data.

Table E-7. Cost components for the two reference case perspectives				
Cost Category	Health Care	Societal	Source(s) of Data	Unit Cost/Monetary Conversion Factor
Costs of intervention delivery	Yes	Yes	Medical records, micro-induction-protocol, and length of stay in hospital for the index hospitalization	Cost per night of hospital stay
Costs of other health care services	Yes	Yes	Non-Study Resources Form (see D.4.1)	Various sources ¹⁴⁴ (e.g., Medicare/ Medicaid data, Kaiser Family Foundation)
Productivity – labor market earnings	No	Yes	Self-reports (see D.4.1)	Hourly wage rates reported at research interviews

Criminal Justice involvement	No	Yes	Criminal Activities Form (see D.4.1)	Unit societal cost estimates for various types of crime ¹⁴⁵
------------------------------	----	-----	--------------------------------------	--

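### Table E-7 does not start the costed index nights at randomisation, so earlier nights inflate each arm's delivery cost and usually add modest, avoidable noise to the cost difference

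*Combined protocol and SAP*

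**What the plan says.** In the Combined protocol and SAP, the intervention-delivery row of Table E-7 (section D.4.1) counts under both the health-care and the societal perspective. Its data source is "Medical records, micro-induction-protocol, and length of stay in hospital for the index hospitalization" and its unit cost is "Cost per night of hospital stay". The table gives no dollar value and does not say from which night the "length of stay in hospital for the index hospitalization" is to be counted.

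Section D.2.4 shows that participants are already inpatients when found. An informatics unit will "produce daily recruitment data lists with identifiable information about hospitalized patients", and once the attending physician agrees, "the research coordinator will approach the hospitalized patient for recruitment". Table E-1 requires "Planned hospitalization for ≥ 48 hours" but sets no limit on nights already spent. Consent and randomisation come after this (D.2.5).

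Section B.9 names one way in which the arm could lengthen the stay: "However, the 5-day microdosing protocol could also delay discharges".

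The cost-model paragraph after Table E-7 plans a mixed generalised linear model, adjusted for site and for patient characteristics that matter to the outcome and may be unbalanced at baseline. Those characteristics are not listed. Quality of life is first measured at baseline (Table E-3), QALYs are an area under that curve, and the horizon is six months (D.4).

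**The concern.** The arm can change the index stay only after randomisation. Nights before that are not delivery of either induction, yet a nightly cost applied to the whole index stay charges them to it. Two things follow.

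- **Cost level.** Aim 3b is to calculate the cost of microdosing as well as its cost-effectiveness. Earlier nights raise the delivery cost reported in each arm. They also lie outside the period over which QALYs accrue, taking the baseline assessment to be made around randomisation.
- **Precision.** The number of earlier nights will differ between participants for reasons unrelated to the arm. That variation enters the incremental cost and, through it, the ICER interval and acceptability curves, unless the model removes it.

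**Working it through.** **Inputs from the documents.** Mean cost per hospitalisation of $37,029 (2011) and $47,480 (2015), with "length of stay remained stable between 5.74-5.82 days" (B.9, a national sample); 135 participants per arm (D.2.12). The cost section states no figure for nightly cost, nights before randomisation or precision, so there is no planned cost figure to reproduce. The factor used below, √(2/135) = 0.1217, does reproduce the detectable effect size in D.2.12: (1.960 + 0.842) × 0.1217 = 0.341, against 0.34 stated (two-sided 5% level assumed).

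**Assumed, because the documents give none.** The SD of nights before randomisation (SD_pre), the SD of nights after it (SD_post), and their correlation r.

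**Step 1. Nightly cost.** 37,029 / 5.74 = $6,451 and 47,480 / 5.82 = $8,158. Each pre-randomisation night therefore adds about $6,450 to $8,160 to a participant's delivery cost.

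**Step 2. Standard error of the cost difference.** For full-stay nights, SD_total = √(SD_pre² + SD_post² + 2·r·SD_pre·SD_post). The SE of the raw difference in means is SD × nightly cost × 0.1217.

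For SD_pre 2, SD_post 5 and r = 0:
- SD_total = √(4 + 25) = 5.39.
- Full stay: SE $4,228 to $5,347.
- From randomisation: SE $3,926 to $4,965.
- Increase: $302 to $382, a ratio of 5.39/5 = 1.077.

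In information terms, 25/29 = 0.86, so about 14% is lost for this cost component: 0.138 × 270 ≈ 37 participants.

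**Step 3. Range.** Increase in SE from using the full stay, at r = 0:

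| SD_pre | SD_post 3 | SD_post 5 | SD_post 7 |
|---|---|---|---|
| 1 | $127–161 | $78–98 | $56–71 |
| 2 | $475–601 | $302–382 | $220–278 |
| 3 | $976–1,234 | $652–825 | $484–611 |

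Over the same grid the increase is $284 to $1,824 at r = +0.3. At r = −0.5 the full stay is equally noisy or less noisy, by up to $911.

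**Step 4. Covariate adjustment.** In a linear model with pre-randomisation nights as a covariate, the residual SD is SD_post × √(1 − r²). The arm coefficient is the same whether the outcome is full-stay or post-randomisation nights, because the two differ only by the covariate. SD in nights for SD_pre 2 and SD_post 5:

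| r | Full stay | From randomisation | With covariate |
|---|---|---|---|
| −0.5 | 4.36 | 5.00 | 4.33 |
| 0 | 5.39 | 5.00 | 5.00 |
| +0.3 | 5.92 | 5.00 | 4.77 |

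A simulation at r = 0 (4,000 trials, 135 per arm) agrees. The SE of the difference in nights was 0.649 for the unadjusted full stay, 0.599 counting from randomisation, and 0.599 for the full stay adjusted for earlier nights.

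**The case against.** The case against is substantial, and most of it limits the size of the point.

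- **No bias.** A reader might infer that the incremental cost is distorted. Randomisation balances earlier nights in expectation, so it is not. This stands.
- **Size.** A reader might infer that the incremental cost carries thousands of dollars of noise, enough to hide a delayed discharge. With SD_pre 2 the per-participant spread is indeed $12,902 to $16,316, but the incremental cost is a difference between means of 135. These nights taken alone then have an SE of $1,570 to $1,986, a 95% half-width of about half a night (1.96 × 2 × 0.1217 = 0.48). Because variances add, the net rise in SE is smaller still.
- **Counting from randomisation can lose precision.** The full stay is less variable whenever r < −SD_pre/(2·SD_post), which is −0.2 for SDs of 2 and 5. This could happen if the admitting condition largely fixes the total stay. It stands against a change of start point alone, but not against the covariate.
- **The planned model may already cover it.** Nights already spent fit the description of the baseline characteristics to be adjusted for. They are not named, however, so nothing commits the analysis to them.
- **The reading is inferred.** Table E-7 lists sources and a unit cost; it does not say outright that every index night is multiplied by that cost. This is the natural reading of the row, but the uncertainty is itself a reason to define the count.

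**Conclusion.** The point holds as a gap in definition with a modest cost in precision. Table E-7 sets no start at randomisation, enrolment follows admission, and earlier nights are not intervention delivery. On the natural reading, each one raises the reported delivery cost in its arm by about $6,450 to $8,160. That figure comes from a national background sample, and how many such nights there will be is not documented.

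The effect on the SE of the cost difference rests wholly on assumed SDs and correlation: about 7.7% ($302 to $382) in the central example, $56 to $1,234 over the zero-correlation grid, and nil or reversed under clear negative correlation. The documents support neither a claim of bias nor a claim that a discharge delay would be swamped. The matter is confined to the economic aim.

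**What to change.** 1. **Main step:** name nights from admission to randomisation as a prespecified covariate in the cost model described after Table E-7. In a linear model this is no less precise than either unadjusted version at any correlation, apart from the negligible cost of estimating one coefficient in 270 participants. With a non-linear link this is a reasonable expectation rather than a guarantee.
2. In the intervention-delivery row of Table E-7, define the costed nights as those from randomisation to discharge of the index stay, in both arms. This makes the reported cost level mean delivery and aligns it with the start of QALY measurement.
3. Report the full index stay by arm descriptively.

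The cost is a few words in the table and one sentence in the analysis text. No new participant data are needed: Table E-7 already calls for length of stay from hospital records, so admission and discharge dates should be obtainable, and the randomisation date comes from the trial's own records.

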Sex as a biological variable. For Aims 1 and 2, we will examine sex as a biological variable by conducting stratified analyses by sex. In addition, we will conduct exploratory analyses to test whether there is a two-way interaction between OUD and pain outcomes and sex.

Exploratory analysis: E₁: During induction, opioid withdrawal and pain will be lower in the microdosing (vs. TAU) arm. We will use EMA data (5 random reports per day: within-individuals, repeated data) to examine if those in the microdosing arm report less opioid withdrawal and pain. Multilevel models will be used where random reports that record changes in opioid withdrawal and pain are assessed within individuals (level 1), and study arm is assessed between individuals (level 2). For example, study arm (level 2: microdosing vs. TAU) will be regressed onto opioid withdrawal (level 1). A significant coefficient for study arm indicates significant differences in overall levels of opioid withdrawal across study arms. We will also describe daily changes (linear or curvilinear) in opioid withdrawal and pain over time by including time (days since the beginning of induction) in the models above. Subsequently, a treatment x time interaction term will be included in models to examine if the trajectory (rates of changes over time) of opioid withdrawal and pain differ across study arms. Separate models will examine opioid withdrawal and pain, and separate models will examine induction (weeks 1, 2) and follow-up (1, 2, 3 months).

E₂: Increases in pain intensity will be associated with illicit opioid use in follow-up. We will use EMA data (5 random reports per day: the within-individuals, repeated data) to examine whether increases in pain are associated with illicit opioid use during the follow-up period (three 1-week bursts). We will use multilevel models to prospectively examine whether pain level at time 1 (T1) predicts illicit self-reported opioid use between T1 & T2, controlling for the previous pain level (T0), age, sex, and use of other pain treatments. In addition, we will include a pain x BUP initiation interaction term to test whether the relationships between pain and subsequent illicit opioid use differ across participants who do and do not initiate BUP treatment.

D.2.12 Power and Sample Size: We will power the study based on the primary outcome of BUP uptake. We plan to enroll 135 participants in each arm. While published case studies report high levels of success with

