microdosing (nearly 100%), we will use a more conservative estimate of treatment uptake from our experience with microdosing (61%). In a controlled trial of standard induction to transition patients with CP from full opioid agonists to BUP, only 24% were successful with BUP uptake.⁵⁸ To detect a difference of this size in BUP uptake, we would only need 27 participants in each arm to assure 80% power. However, we will recruit a larger sample to account for the possibility that uptake will be greater than 24% in the TAU arm (see **Table E-5**). Even with study attrition, we will be

able to assess BUP uptake for all participants based on medical record extraction,

For pain outcomes, we based our power calculations on expected changes in pain intensity from baseline to 3 months. Our pilot data (see D.1.1) suggests that mean (SD) pain intensity score will be 7.3 (± 1.6) at baseline for all participants. With a sample of 270 participants (135 per arm), the minimum effect size (Cohen's d) that can be detected with power of 80% is 0.34. This effect size corresponds to a difference between arms (microdosing vs. TAU) of 8.4% for participants'

reduction in pain scores (assuming that the SD of change is 1.8). Note that the SD for the pain score change is greater than that of the pain intensity score at each time point due to the intra-participant correlation in pain intensity over time. Because pain reduction is only considered for participants with BUP uptake, attrition is already incorporated into these estimates.

D.3 Aim 3a) Examine factors influencing reach, adoption, implementation, and maintenance of the microdosing protocol.

D.3.1 Overview and hypotheses. In this hybrid type 1 effectiveness-implementation trial, we will use RE-AIM and CFIR frameworks to guide Aim 3a, in which we will use qualitative and quantitative methods to describe multi-level factors influencing reach, adoption, implementation, and maintenance of BUP microdosing.

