D.4.1 Measures: Health-related quality of life (HRQoL) will be measured with the Patient-Reported Outcomes Measurement Information System (PROMIS).^{135,136} The PROMIS-Preference (PROPr) scoring system uses the respondent's scores for each of 7 PROMIS domains to calculate a health utility index value that represents the general US population's preference for the respondent's current health state: Cognitive Function–Abilities, Depression, Fatigue, Pain Interference, Physical Function, Sleep Disturbance, and Ability to Participate in Social Roles and Activities.^{122,137} Construct validity for PROPr has been demonstrated using the EQ-5D-5L, the HUI, and two large datasets from the general US population.¹²⁴ The health-utility value is then used to calculate QALYs, as investigators from CHERISH, and many others have done in similar studies.¹³⁸⁻¹⁴²

Measures of employment status, work hours and hourly wage rates: At baseline, 1,3, and 6-months, we will collect data on employment status, and if employed, number of hours typically worked in a week and hourly wage rates, by adapting instruments developed and tested by CHERISH researchers in previous OUD studies.

Measures of criminal activities: At baseline, 1,3, and 6-months, we will collect data on criminal activities (in the past 3 months) in order to assess related societal costs, including criminal justice system-related costs (policing, prosecution, incarceration, etc.) and tangible and intangible costs to the victims. We will collect self-reported data on crimes committed for each major type of crime frequently reported by people with OUD.¹⁴³

Measures of health care utilization outside the intervention: At baseline, 1,3, and 6-month health care utilization outside the intervention (including inpatient, outpatient, emergency services, and medications) during the past 3 months will be self-reported using a Non-Study Resources Form customized for this study. Use of non-medical resources (e.g., travel time to medical care) will also be self-reported and collected.

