For each reference case perspective, to estimate the incremental HRQoL and costs associated with the intervention – BUP microdosing vs. TAU – we will use intent-to-treat design and estimate a mixed Generalized Linear Model of the HRQoL/costs at the patient-level and at each assessment point as a function of patient assignment to microdosing (vs TAU), site fixed effects, and patient characteristics bearing implications for the outcomes but possibly not balanced at baseline, with random effects at patient and site levels.¹⁴⁶ The method of recycled predictions will be used to obtain predicted mean values for HRQoL and each cost category, by study arm. QALYs gained will be estimated using the area under the curve methodology.¹⁴⁷⁻¹⁴⁹ Predicted costs from different cost categories will be summed and tested according to relevant perspectives.¹⁴⁹ We will derive predicted *incremental* costs for intervention vs TAU for each individual patient based on the estimated models.

Cost-effectiveness analysis (CEA) will estimate an incremental cost-effectiveness ratio (ICER) associated with BUP microdosing vs. TAU. The ICER will be calculated by dividing (mean) incremental cost associated with microdosing vs TAU by (mean) incremental effectiveness. Sampling uncertainty in the estimated ICER will be taken into account by bootstrapping the study sample of the individual-level incremental cost and incremental effectiveness estimates and deriving non-parametric confidence intervals. We will further construct ICER acceptability curves for both reference case perspectives. Acceptability curves display the probability that an ICER would fall below a given willingness to pay for an incremental unit of the desired outcome and thus be considered a good value (that is, cost-effective).^{150,151}

D.5 Design considerations and limitations:

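### The Aim 3b models should always adjust for baseline PROPr utility and baseline-period cost, and should treat baseline as a covariate rather than one of the modelled responses.

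*Combined protocol and SAP*

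**What the plan says.** Section D.4 (Aim 3b), in the paragraph after Table E-7, specifies a mixed generalized linear model for HRQoL and for costs, at patient level and at each assessment point. The regressors are arm, site and "patient characteristics bearing implications for the outcomes but possibly not balanced at baseline", with random effects for patient and site. Arm means come from recycled predictions, and "QALYs gained will be estimated using the area under the curve methodology". No patient characteristic is named. No time term and no arm-by-time term are listed.

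Both baseline measures exist. Table E-3 (Section D.2.8) schedules PROPr at 0, 1, 3 and 6 months. Section D.4.1, in its paragraph on health care utilisation outside the intervention, has participants report the past 3 months of use at baseline, 1, 3 and 6 months. Randomisation (Section D.2.5) is stratified by OUD severity, heroin use and mood disorder, but not by utility or prior cost.

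For scale, Section D.2.12 says "We plan to enroll 135 participants in each arm" and gives a minimum effect size for pain intensity "that can be detected with power of 80% is 0.34". The documents give no PROPr SD, between-visit correlation, cost SD or expected QALY effect.

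**The concern.** The QALY difference is the denominator of the ICER, on which H5 rests. Over a 6-month horizon it is bounded by half a year times the utility difference, so it will be small. Baseline utility is normally the strongest predictor of later utility. If it is left out, a chance difference between arms at baseline enters the area under the curve through the baseline visit itself, and again through its correlation with the three later scores. A patient random effect does not remove a difference between arms.

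There is a second difficulty. If baseline is a modelled response and arm has one coefficient, that coefficient averages over a visit at which no treatment effect can exist. What is at stake is precision, dependence on this trial's chance imbalance, and an open choice of covariates in an open-label trial.

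**Working it through.** **The plan's own figures.** Taking two-sided alpha of 0.05 (not stated with the power calculation), the minimum detectable d with 135 per arm is (1.960 + 0.842) × √(2/135) = 2.802 × 0.1217 = 0.341. This matches the stated 0.34. For 61% against 24% uptake, the pooled two-proportion formula gives (1.960 × √(2 × 0.425 × 0.575) + 0.842 × √(0.61 × 0.39 + 0.24 × 0.76))² / 0.37² = 26.8, so 27 per arm, as stated.

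**Inputs.** From the documents: 135 per arm, PROPr at 0, 1, 3 and 6 months, d = 0.34, and uptake of 61% and 24%. Assumed: PROPr SD of 0.20 to 0.25, and equal between-visit correlation r of 0.4 to 0.6.

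**Area-under-the-curve weights.** The trapezoid rule gives 0.5, 1.5, 2.5 and 1.5 months (sum 6). The squared weights sum to 0.25 + 2.25 + 6.25 + 2.25 = 11, and the post-baseline weights sum to 5.5.

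**Effect of adjustment on variance (raw-score area, SD units, months).**
- Variance of the area = 11(1 − r) + 36r.
- Covariance of the area with baseline = 0.5 + 5.5r.
- Adjusted/unadjusted variance = 1 − covariance²/variance. The SD cancels.

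| r | Variance | Covariance | Ratio | Variance removed |
|---|---|---|---|---|
| 0.4 | 21.0 | 2.70 | 0.653 | 35% |
| 0.5 | 23.5 | 3.25 | 0.551 | 45% |
| 0.6 | 26.0 | 3.80 | 0.445 | 56% |

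At SD 0.25 and r = 0.5, the standard error of incremental QALYs falls from 0.0123 to 0.0091.

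**Size of a chance shift.** The standard error of the baseline difference is SD × √(2/135), which is 0.0243 at SD 0.20 and 0.0304 at SD 0.25. The shift is that value × covariance/12.
- Low end: 0.0243 × 2.70/12 = 0.0055.
- High end: 0.0304 × 3.80/12 = 0.0096.

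At the 84% retention cited in Section D.2.6 (about 113 per arm), these are about 9% larger.

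**Against an effect size.** Carrying d = 0.34 over to utility from month 1 to month 6 (an assumption), the shift as a share of the effect is 0.1217 × (0.5 + 5.5r)/(0.34 × 5.5). This is 18%, 21% and 25% for r = 0.4, 0.5 and 0.6, whatever the SD. If instead those who start BUP gain 0.05 to 0.10 in utility (assumed), the effect is 0.37 × 0.05 to 0.10 × 5.5/12 = 0.0085 to 0.0170 QALY. At SD 0.20 and r = 0.6 the shift is 0.0077, or 45% to 91% of that effect.

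**Single arm coefficient.** Take the listed terms literally, with complete data, an identity link and baseline as a response. The arm coefficient is then the mean of four visit differences. A baseline difference D enters incremental QALYs as 0.5 × (1 + 3r)/4 × D, which is 0.31D at r = 0.5. The raw-score area gives 3.25/12 = 0.27D. A constant post-baseline utility gain g contributes 0.5 × 3/4 × g = 0.375g instead of 5.5/12 × g = 0.458g.

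**The case against.** The case on the other side has several parts.

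- **The covariate phrase.** A reader might infer that the plan adjusts only when imbalance is observed. The text does not say so. Its leading condition is prognostic relevance, the word used is possibly, and no test or threshold is given. The explicit rule of adding variables that differ by arm belongs to the additional analyses of Aims 1 and 2 (Section D.2.11). Baseline utility could fall within the Aim 3b phrase. This stands; what remains is that neither baseline measure is named, so nothing commits the analyst to either.
- **Bias.** A reader might infer that the QALY difference is biased by baseline imbalance. Over randomisation the unadjusted raw-score comparison is not; a simulation gave a mean of about zero. The planned bootstrap intervals and acceptability curves would also show the lost precision.
- **Size.** A reader might infer that the shift is as large as the likely effect. The documents give no utility SD, correlation or expected QALY effect, so this cannot be shown. It is so only if the QALY effect is about 0.01 to 0.015 or less.
- **Estimator.** The variance and shift figures apply to a raw-score area, whereas the plan uses recycled predictions from a mixed model. This stands; the figures indicate scale.
- **Costs.** A reader might infer that the same magnitude holds for costs. No cost SD is given, and nothing says pre-enrolment costs are summed into incremental cost. However, a 3-month recall at month 1 covers about two months before enrolment, so prior use can reach a modelled response.
- **Stratification.** Stratifying by mood disorder may slightly limit utility imbalance, since depression is one of the seven PROPr domains.

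**Conclusion.** The point holds as a matter of precision and pre-specification. Baseline PROPr and baseline 3-month cost are collected but not named as covariates, the role of the baseline visit is undefined, and no arm-by-time term is listed.

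For a raw-score area, adjusting for baseline utility would remove about 35% to 56% of the variance of incremental QALYs. This rests only on equal between-visit correlation of 0.4 to 0.6. The one-standard-error shift of about 0.005 to 0.010 QALY rests also on an assumed SD of 0.20 to 0.25. It is about a fifth to a quarter of the effect at d = 0.34.

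That benchmark is a minimum detectable effect for pain, not an expected effect on utility. If benefit passes only through the 37-point uptake difference, those who start BUP would need to gain 0.34/0.37 = 0.92 SD. The pilot's uncontrolled fall in pain was (7.3 − 6.0)/1.6 = 0.81 SD, and pain interference is only one PROPr domain. A smaller effect, and so a larger share, is plausible but not established. The cost side is a gap without a computable size. It should be settled before analysis.

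**What to change.** Amend the model paragraph of Section D.4 as follows.

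1. Include baseline PROPr as a fixed covariate in the HRQoL/QALY model, and the baseline 3-month cost in the matching cost model, whatever the observed balance. List any other covariates by name.
2. Use only post-baseline visits as responses, with time and arm-by-time terms. A longitudinal model that keeps baseline as a response but constrains the arm means to be equal there is an acceptable equivalent.
3. Set the same baseline utility for both arms when computing the area under the curve.
4. State how month-1 costs are handled, given that the 3-month recall reaches back before enrolment.

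This costs SAP wording only. Both baseline measures are already collected, and neither sample size nor visit schedule changes. The wording should be fixed before outcome data by arm are examined.
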